Title

**COMPARISON OF OUTCOME BETWEEN GRISOTTI FLAP
VERSUS REVERSE MIRROR GRISOTTI FLAP FOR
CENTRAL QUADRANT BREAST TUMORS**

Submitted By:

[name]

Senior Registrar

Department of General Surgery,

Mayo Hospital, Lahore

Dated:

26TH NOVEMBER, 2025

INTRODUCTION:

Breast cancer amongst women is the most common cancer and the second leading cause of deaths related to cancer worldwide.⁶ Its incidence is rising by 1% annually during 2012–2021, largely confined to localized-stage and hormone receptor-positive disease.¹ A steeper increase in women < 50 years (1.4% annual) versus \geq 50 years (0.7%) overall was significant only among White women. African/Pacific Islander women had the fastest increase in both age groups (2.7% for women <50 years and 2.5% for women \geq 50 years per year)¹. Hence, young Asian ,American/Pacific Islander women had the second lowest rate in 2000 (57.4 per 100,000) but the highest rate in 2021 (86.3 per 100,000).¹

In a multitude of developed and emerging countries, including Pakistan, breast cancer is a cause of significant morbidity and mortality.^{1,2} The average age of developing a breast cancer among white American women is 61 years, however the average age for Pakistani women is 51.4 years.²

In the past, mastectomy was treatment of choice for any stage of breast cancer.⁹ However newer advancements resulting in early diagnosis, providing advanced systemic therapies and easy availability of radiotherapy facilities have paved the paths for breast conservations.^{7,9} Sometimes the size and location of the tumor leads to undesired aesthetic results which can be encountered when attempting resections with safe margins. The major part of the aesthetic problem after breast conservation surgery is due to large glandular defects and scars contractures.¹⁵ This is where oncoplastic techniques are used for the repair of resulting glandular defects without compromising the oncological outcomes.^{7,9,15}

Breast oncoplastic surgery, integrating oncologic and plastic surgery principles, is increasingly prevailing in developed as well as developing countries. The technique involves precise and thorough planning of incisions,excisions, glandular reshaping and nipple areolar complex (NAC) repositioning for improved and symmetrical aesthetic

outcomes.³ Oncoplastic breast surgery has hence become the standard of care in breast cancer owing to its feasibility, advances and oncological safety.⁵

Among the different quadrant tumours, centrally located breast tumours (CLBT) account for about 5–20% of all breast cancer cases.^{7,9} Because of their location CLBT pose special oncological and aesthetic concerns. Selecting an optimal surgical approach for CLBT remains debated till date, reflecting the complexity of balancing oncologic principles with aesthetic outcomes and local control.³ The resection of NAC is almost always necessary in central quadrant tumours and aesthetic outcomes are mostly poor if only a standard breast conservative therapy is performed.¹⁴

Oncoplastic approaches for centrally located breast tumours may include Grisotti flap, reverse mirror grisotti flap, latissimus dorsi flap, inferior pedicle flap, Melon slice, and round block techniques¹⁶. For centrally located breast tumours Grisotti flap technique has a short learning curve, quick to perform, with a low complication rate, satisfactory cosmetic outcome and no loss of body image in the post-operative period making it a more physiological procedure.^{7,13} The oncologic outcome of oncoplastic breast conservation was shown to be comparable to the classical mastectomy in cases of central breast tumors¹⁰. The Grisotti technique consists of excising central quadrant breast tumor alongwith nipple areolar complex and mobilizing a dermo-glandular flap which is de-epithelialized, rotated and advanced based on inferior and lateral pedicle in order to fill the glandular defect and reshape the breast, recreating a neo-areola.^{8,9} Grisotti flap is a partial mastectomy and an immediate volume replacement technique¹⁰. The Grisotti flap technique demonstrated superior patient satisfaction alongwith aesthetic and psycho-social outcomes while maintaining oncological safety that is comparable to that of mastectomy. Hence Grisotti flap technique is a standard alternative to mastectomy, particularly in patients prioritizing aesthetic outcomes.^{4,6} Advances in oncoplastics have devised the modification of this original technique which involves the utilizing other vascular pedicles for the dermoglandular advancement and rotation.⁹

A reverse-mirror Grisotti flap, also known as a Reverse-Bay of Bengal modification, is a variation of the Grisotti flap technique used in breast cancer surgery. It is designed to reconstruct defects in the central breast quadrant after a breast conservation surgery. This modification involves re-orienting the flap medially where it is dependent mainly on the perforators of internal mammary artery for blood supply, potentially offering better aesthetic results and more versatile and robust blood supply. The Grisotti flap, despite its well known utility, has limitations, particularly in patients with non-ptotic breasts, where it may lead to fullness laterally and suboptimal cosmesis, the Reverse Bay of Bengal modification of the Grisotti flap is designed to address these limitations by preserving chest wall perforators and avoiding excessive lateral bulging.¹¹ This technique hence offers a more cosmetic alternative for patients with central quadrant tumors requiring nipple-areola complex (NAC) excision.¹¹

OBJECTIVES:

To compare the outcome between grisotti flap versus reverse mirror grisotti flap in terms of flap viability, cosmetic outcome (visual analogue scale) and seroma formation.

OPERATIONAL DEFINITIONS:

1. Centrally located breast tumors (CLBT):

Tumors that are completely or partially located in the projection of the areola up to the chest wall and/or within 2 cm around the areola

2. Grisotti Flap:

The Grisotti flap is a local rotational flap used to reconstruct defects after removing a central breast cancer, often involving the nipple-areola complex (NAC). It uses tissue from the inferior pole of the breast to fill the central defect.

3. Reverse-Mirror Flap:

The reverse-mirror version is a modification where the flap is flipped and reoriented, using the internal mammary vessels as the primary blood supply.

4. Flap viability:

Absence of necrosis of new areola formed as seen clinically at 48 hours and 7th day postoperatively.

Flap viability categories:

A (None): No necrosis.

B (Color Change): Color change suggesting impaired perfusion or ischemic injury.

C (Partial Thickness): Partial thickness skin flap necrosis resulting in wound breakdown.

D (Full Thickness): Full thickness skin flap necrosis.

5. Cosmetic outcome:

Cosmetic outcome will be explained with VAS (visual analogue scale) by the patient. The scale will range from 0-10 with 0 being categorized as worst cosmetic outcome and 10 being categorized as best cosmetic outcome.

6. Seroma formation:

Seroma formation is the visible swelling at the operative site which will be confirmed and quantified by ultrasound on 7th post operative day with volume more than 20ml.

HYPOTHESIS:

There is a difference in the outcome between Grisotti versus Reverse Mirror Grisotti flap in centrally located breast cancers.

MATERIAL AND METHODS:

STUDY DESIGN: Randomised Control Trial

SETTING: SURGICAL FLOOR, MAYO HOSPITAL LAHORE.

DURATION OF STUDY: 06 months after approval of synopsis.

SAMPLE SIZE: Sample size of 106 patients (53 patients in each group) is estimated by using 95% confidence level, 10% absolute precision with expected percentage satisfaction rate in group A as 90% and in group B as 95%.

$$n = \frac{Z_{1-\alpha/2}^2 (P_1(1-P_1) + P_2(1-P_2))}{d^2}$$

$$d^2$$

$$Z_{1-\alpha/2} = \text{confidence level } 95\% = 1.96$$

$$P_1 = \text{population proportion A} = 90\%^{14}$$

$$P_2 = \text{Population proportion B} = 95\%^8$$

$$d = \text{absolute precision } 10\%$$

SAMPLING TECHNIQUE: computer generated random table.

SAMPLE SELECTION:

Inclusion Criteria:

1. Diagnosed cases of breast cancer patients
2. Gender: Females
3. Age: 25-70 years
4. T1 (<2cm) and T2 (2-5cm) tumors with or without prior systemic therapy
5. Tumor located in the NAC or located within 2 cm of the edge of the areola

Exclusion Criteria:

1. Metastatic breast cancer
2. Inflammatory breast cancer
3. Patients not willing for post-operative radiotherapy
4. High tumour-breast ratio

DATA COLLECTION PROCEDURE:

The study approval will be taken from the Ethical Committee of the King Edward Medical University, Lahore and will be performed in accordance with the current revision of the Helsinki Declaration. Informed consent will be obtained from all individual participants with diagnosis of central quadrant breast tumors as per operational definition, and data will be collected on predesigned proforma. Patients will be divided into two groups, Grisotti flap (group A) and Reverse Mirror Grisotti Flap (group B). Patients will be recruited from OPD of Mayo hospital during the same study period.

Patients fulfilling the inclusion criteria will be randomly divided into either group. Pre-operative marking will be done in standing position. All procedures will be done under general anesthesia. Circumareolar incision will be given for excision of tumor alongwith nipple areolar complex. New areola will be marked beneath the previous nipple areolar complex and de-epithelialisation of infra-neo-areolar skin will be done . In group A, the dermoglandular flap will be raised on infero-lateral perforators of intercostal arteries and will be rotated and advanced to fill the gap . In group B, the dermoglandular flap will be raised on the medial perforators of internal mammary artery and will be rotated and advanced to fill the defect. In both groups, glandular approximation will be done with vicryl 3-0 interrupted sutures and skin will be closed with prolene 4-0 subcuticular sutures. Axillary lymph node dissection or sentinel lymph node biopsy will be done as indicated in each patient.

Post operatively flap viability will be assessed at 48 hours and on 7th day. Cosmetic outcome will be assessed using visual analogue scale on 7th postoperative day. Seroma formation will be assessed on 7th day post-operatively.

DATA ANALYSIS PRODECURE:

All the collected data will be entered and analyzed by using Statistical Package for the Social Sciences (SPSS,25). Quantitative data (cosmetic outcome with VAS) will be expressed as mean (M) \pm S.D. Independent T test will be used for comparing means for cosmetic outcome. Qualitative data (tumor size, flap viability and seroma formation) will be expressed as frequencies and percentages. Chi square (χ^2) test will be used to compare between groups for qualitative data. The association between type of procedure used and clinical outcome variable will be assessed by using Odds Ratio (OR) with 95% confidence interval (CI). The P value will be considered significant if it is less than 0.05.

OUTCOME & UTILIZATION:

Breast conservation surgery is equivalent to mastectomy for early stage breast cancer patients. Central quadrant tumours can be treated with various oncoplastic techniques with a satisfactory aesthetic outcome and low morbidity. Grisotti flap and reverse mirror grisotti flap are the favourable viable surgical options for central quadrant breast tumours.

REFERENCES:

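### The 53 per group is justified by precision on a satisfaction rate that no outcome, data item or analysis named in the protocol uses

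*Protocol*

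**What the plan says.** Under MATERIAL AND METHODS, SAMPLE SIZE, the protocol sets 106 patients, 53 per group. It uses a 95% confidence level, 10% absolute precision and an "expected percentage satisfaction rate in group A as 90% and in group B as 95" per cent. The formula gives the precision of a difference between two proportions and has no power term.

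The rest of the protocol works with other quantities:

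- **OBJECTIVES** compares the flaps "in terms of flap viability, cosmetic outcome (visual analogue scale) and seroma formation".
- **OPERATIONAL DEFINITIONS, item 5** has the patient score the cosmetic result: "The scale will range from 0-10 with 0 being categorized as worst cosmetic outcome and 10 being categorized as best cosmetic outcome". No score is designated as satisfied.
- **DATA ANALYSIS** states: "Independent T test will be used for comparing means for cosmetic outcome". It also states: "Qualitative data (tumor size, flap viability and seroma formation) will be expressed as frequencies and percentages", and that a chi-square "test will be used to compare between groups for qualitative data". It adds: "The association between type of procedure used and clinical outcome variable will be assessed by using Odds Ratio (OR) with 95% confidence interval (CI"), without saying which variable is meant. Significance is set at P below 0.05.
- **HYPOTHESIS** reads: "There is a difference in the outcome between Grisotti versus Reverse Mirror Grisotti flap in centrally located breast cancers".
- **Data Collection Proforma** has outcome rows for flap viability (A to D, at 48 hours and day 7), cosmetic VAS and seroma (yes/no). It has no satisfaction item.

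**The concern.** A sample-size statement should tell the reader what the trial can deliver on the comparison it was built for. Here the only justification for 106 patients concerns a binary variable that appears nowhere among the definitions, the assessments, the proforma or the named analyses. The nearest outcome, the patient-scored VAS, is analysed as a mean. Precision on a proportion says nothing about precision on a mean unless an SD is given, and none is.

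Three outcomes, one of them read at two time points, stand side by side with no primary. The protocol states a hypothesis of a difference and a significance threshold, but no size of difference for any outcome. A non-significant result on VAS, viability or seroma would then have no pre-stated target behind it, and a reader could not tell which result the 106 patients were meant to secure.

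**Working it through.** **1. The protocol's own figure.** Inputs from SAMPLE SIZE: z = 1.96, P1 = 0.90, P2 = 0.95, d = 0.10.

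n = 1.96² × (0.90 × 0.10 + 0.95 × 0.05) / 0.10² = 3.8416 × 0.1375 / 0.01 = 52.8, so 53 per group and 106 in total. The figure reproduces. At n = 53 the half-width is 1.96 × √(0.1375/53) = 0.0998, or 10.0 points on the difference between the two rates.

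**2. Does any planned analysis use that quantity?**

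| Outcome | Form in the protocol | Named analysis | Expected value given |
|---|---|---|---|
| Satisfaction rate | not defined or recorded | none | 90% and 95% |
| Cosmetic VAS | 0-10 score | t test on means | none |
| Flap viability | A to D, two time points | chi-square | none |
| Seroma | yes/no | chi-square | none |

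The only quantity with expected values is the only one without an analysis.

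**3. What 53 per group gives on the VAS.** Independent t test, two-sided 5%, 104 degrees of freedom, noncentral t: 80% power at 0.549 SD and 90% at 0.636 SD. The 95% CI half-width is t(0.975, 104) × √(2/53) = 1.983 × 0.1943 = 0.385 SD. The protocol gives no SD, so the SDs below are assumptions and the 1-point difference is only illustrative.

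| Assumed SD (points) | Difference detectable at 80% power | Power for 1 point |
|---|---|---|
| 1.5 | 0.8 | 93% |
| 2.0 | 1.1 | 72% |
| 2.5 | 1.4 | 53% |
| 3.0 | 1.6 | 40% |

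**4. What it gives on seroma.** Half-width = 1.96 × √(2p(1−p)/53) for an assumed common rate p. The detectable rates use the pooled normal approximation, which is rough at low rates.

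| Assumed rate | 95% CI half-width | Detectable at 80% power |
|---|---|---|
| 5% | 8.3 points | 5% vs 24% |
| 10% | 11.4 points | 10% vs 32% |
| 20% | 15.2 points | 20% vs 45% |
| 30% | 17.4 points | 30% vs 57% |

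The half-width equals 10 points at p of about 7.5%.

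**5. Flap viability.** The half-width formula in step 4 would apply to any two-way split. It cannot be evaluated for viability until the time point, the split of A to D and an expected rate are fixed. Category B, colour change, is not clearly on either side of absence of necrosis.

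**6. If satisfaction were analysed exactly as assumed.** The half-width of 10.0 points is twice the assumed 5-point difference, so the expected interval runs from −5 to +15 points. The odds ratio is (0.95/0.05)/(0.90/0.10) = 2.11. At the expected counts its log has standard error √(1/50.35 + 1/2.65 + 1/47.7 + 1/5.3) = 0.779, giving a 95% CI of 0.46 to 9.7. Power at two-sided 5% is about 15% by exact enumeration of the uncorrected chi-square and 16% by normal approximation. For 80% power about 435 per group would be needed.

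**The case against.** Sizing for precision is a legitimate approach, and the formula does not depend on what the two proportions are called. It would give the same 10 points for seroma or a viability split if their rates were near 5% and 10%, or 95% and 90%. That is correct, but the protocol gives no expected rate for either outcome and makes no such link.

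A charitable reader could take satisfaction to mean the VAS, since the patient scores it and the introduction mentions patient satisfaction together with aesthetic outcome. A satisfied proportion could then be derived from data already collected, and the odds-ratio sentence could be its analysis. This makes the gap one of definition rather than an unobtainable endpoint. It does not close the gap: there is no cut-off and no stated link, and the odds-ratio sentence names no variable.

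It is also fair to say that the 15-16% power and 435 per group judge a precision calculation by a power standard it did not claim. Those figures should not be read as showing the trial too small. They matter only as a caution against adding a satisfied/not satisfied endpoint to match the existing paragraph.

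Finally, quoting a detectable difference for an n already chosen does not by itself supply a target. That stands, and the fix below therefore also asks for the difference the sponsor considers relevant.

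**Conclusion.** The concern holds and should be fixed. The stated basis for 106 patients is arithmetically right but attached to a quantity that the protocol does not define, record or analyse. No primary outcome or target difference is named in its place. This mismatch lies within the protocol itself and is not a detail left to a statistical analysis plan.

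It is not shown that 53 per group is inadequate. On the VAS, adequacy turns on an SD the protocol does not give: across assumed SDs of 1.5 to 3 points, power for a 1-point difference runs from 93% down to 40%. On seroma, the stated precision holds only at an assumed common rate of about 7.5% or less. The odds ratio's confidence interval will still show what the data exclude for whichever binary variable it is applied to. What is missing is a pre-stated standard for judging n.

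**What to change.** 1. Name one primary outcome and its time point.
2. Rewrite SAMPLE SIZE on that outcome, stating the difference or precision regarded as relevant.
   - *Cosmetic VAS* (the outcome nearest to satisfaction): replace the 90% and 95% inputs with wording such as: With 53 per group, the independent t test (two-sided alpha 0.05) has 80% power for a mean difference of 0.55 SD (90% for 0.64 SD) and a 95% CI half-width of 0.39 SD. Add the assumed SD in points and its source.
   - *Seroma*: state the expected rate in each group and the resulting 95% CI half-width at 53 per group.
   - *Flap viability*: first fix the time point and which of categories A to D count as viable, then state the same.
3. Name the variable or variables in the odds-ratio sentence.

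A dichotomised satisfied proportion is not recommended. If it is kept, define the VAS cut-off, add it to the analysis, and state that 53 per group has only about 15-16% power for 90% versus 95%. In that case the sponsor should also confirm that reference 8, whose title concerns the Grisotti procedure, supports the Group B rate. The source was not available, so this is a query only.

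The cost is a reworded paragraph, one sentence naming the primary outcome, and a variable name; no new data item is needed. The sponsor must source an SD or event rates, and the restated figure may look less favourable than 10% precision. The number of patients stays at 106 unless the relevant difference is smaller than the detectable one. The protocol must then say so or reconsider n, which would bear on its six-month duration.

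### The day-7 cosmetic VAS is fixed as an unadjusted t test; adjusting for age, T category and prior systemic therapy would be a cheap gain in efficiency of unknown, probably modest size

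*Protocol*

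**What the plan says.** The data analysis section of the protocol names the method for the only continuous outcome: "Independent T test will be used for comparing means for cosmetic outcome". It adds that "The P value will be considered significant if it is less than 0.05". No adjusted analysis is described, and a confidence interval is promised only for the odds ratio. The score is a 0-10 patient rating taken once, on day 7; no pre-operative score is described.

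The hypothesis has no direction: "There is a difference in the outcome between Grisotti versus Reverse Mirror Grisotti flap in centrally located breast cancers". The sample size is stated as "Sample size of 106 patients (53 patients in each group"), derived from "10% absolute precision" around satisfaction rates of 90% and 95%. It contains no power term, no SD for the VAS and no target difference in VAS.

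The population is mixed by design. Ages run from 25 to 70, and the inclusion criteria admit "T1 (<2cm) and T2 (2-5cm) tumors with or without prior systemic therapy". The introduction names tumour size and location as reasons why resection with safe margins can give an unwanted aesthetic result. The data collection proforma has a field for age and blanks for stage and chemotherapy status. It has no separate field for T category.

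**The concern.** When a continuous outcome varies with patient features that are known before randomisation, an unadjusted comparison leaves that variation in the error term. Here T category has to be known to apply the inclusion criteria, prior systemic therapy is named in the same criterion, and age is recorded. The protocol gives its own reason to expect tumour size to matter for cosmesis.

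At stake is the width of the confidence interval for the VAS difference, in a trial whose size was never set for that comparison. Allocation is by a computer-generated random table with no stratification described, so these features may also differ between groups by chance. Adjustment would deal with both without adding patients. Because the protocol commits to a named test, the change is best made before any data are seen; made later, an adjusted main analysis would look chosen after the fact.

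**Working it through.** **Inputs from the protocol.** 53 per group, 106 in all; significance level 0.05, taken as two-sided because the hypothesis is non-directional and the sample-size formula uses 1.96; satisfaction rates 90% and 95%; absolute precision 10%.

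**Assumptions, not in the protocol.** A true VAS difference of 0.5 SD, and a share R² of VAS variance explained by the covariates of 0 to 0.20.

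**1. The plan's own figure.** n = 1.96² × (0.90×0.10 + 0.95×0.05) / 0.10² = 3.8416 × 0.1375 / 0.01 = 52.82, rounded up to 53 per group and 106 in total. It reproduces, but it concerns the precision of a difference in proportions, not the VAS.

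**2. The planned t test.** The standard error of the difference, in SD units, is √(2/53) = 0.194. At 0.5 SD the non-centrality is 0.5/0.194 = 2.574. With 104 degrees of freedom, two-sided power is 72.2%. The difference detectable with 80% power is 0.549 SD. (The normal approximation gives 73.0% and 0.544 SD.)

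**3. The adjusted model.** With k = 3 covariates, the variance of the group difference is multiplied by about

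V = (1 − R²) × (N − 3)/(N − 3 − k) = (1 − R²) × 103/100.

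The interval width is multiplied by √V, the equivalent group size is 53/V, and the non-centrality at 0.5 SD is 2.574/√V.

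| Assumed R² | V | Interval width × | Equivalent n per group | Power at 0.5 SD |
|---|---|---|---|---|
| t test, no covariates | 1 | 1 | 53 | 72.2% |
| 0 | 1.030 | 1.015 | 51.5 | 71.0% |
| 0.05 | 0.979 | 0.989 | 54.2 | 73.1% |
| 0.10 | 0.927 | 0.963 | 57.2 | 75.4% |
| 0.20 | 0.824 | 0.908 | 64.3 | 80.2% |

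**4. Break-even.** V = 1 when R² = 1 − 100/103 = 0.029. Below about 0.03 the model loses slightly; above it, it gains. Leaving out the factor 103/100 would overstate the benefit: at R² of 0.10 and 0.20 it would give intervals 5% and 11% narrower and power of 77% and 81%.

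**5. Chance imbalance.** For a feature present in half of the patients (assumed), the standard error of the between-group difference in its frequency is √(2 × 0.25/53) = 0.097. A gap of 15 percentage points or more is 0.15/0.097 = 1.54 standard errors, so its probability is about 12%.

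**The case against.** The strongest reply is that nothing here is wrong. After randomisation the t test is valid and unbiased, and its interval already allows for chance imbalance. A reader might infer from the mixed population that the unadjusted comparison is biased or in error; the protocol does not support that. A covariate list is also commonly left to a statistical analysis plan, which may exist. All of this stands. The protocol does, however, name a specific test rather than stay silent, so a change to the main method belongs here.

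Second, a reader might take the gain as established and free. It is neither. No passage says how strongly age, T category or prior systemic therapy predicts a patient's own rating on day 7. The remark on tumour size is general and unquantified, and there is no baseline score to adjust for. The 0.5 SD difference is not in the protocol either. If R² is below about 0.03, adjustment costs a little.

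Third, some fields on the proforma are unsafe as covariates. The blanks for stage and chemotherapy status carry no definition or date. Stage could be filled in from surgical pathology, and chemotherapy status could reflect treatment after the operation. This objection stands against those two fields, but not against values fixed at eligibility.

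Fourth, the introduction most directly ties poor cosmesis after a Grisotti flap to non-ptotic breasts, and the proforma has no field for ptosis or breast size. That limits what adjustment on the present form can achieve. It is no reason to ignore the variables that are known.

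**Conclusion.** The point holds as a low-cost recommendation, not as the correction of an error. The planned t test may stand as a valid analysis; a short prespecified regression would probably be somewhat more precise.

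The size of the gain is unknown. Over assumed R² of 0.05 to 0.20 it is an interval about 1% to 9% narrower and about 1 to 8 power points at an assumed 0.5 SD difference. If the covariates explain nothing, the loss is about one power point and the interval is about 1.5% wider. That balance favours adjustment, provided the list is short and every covariate is fixed before randomisation. It does not make up for the VAS comparison never having been sized.

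**What to change.** In the data analysis section, make the main VAS analysis a linear regression of the day-7 score on randomised group with three covariates fixed before data are seen: age, T category (T1 or T2 as judged at eligibility) and prior systemic therapy (yes/no). Report the adjusted mean difference with its 95% confidence interval, and keep the t test as a supporting analysis. Leave flap viability and seroma unadjusted.

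On the proforma, add dated pre-operative entries for T category and prior systemic therapy, so that neither a post-operative stage nor a later chemotherapy status is used in their place. Do not enter the rest of the proforma: break-even R² rises to about 0.05 with five covariates (5/103) and 0.10 with ten (10/103).

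The cost is a few sentences in the analysis section and two lines on the form. No extra patients or visits are needed, and the named software, SPSS, runs the model.

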15. Emiroğlu M, Sert İ, İnal A. The role of oncoplastic breast surgery in breast cancer treatment. *The journal of breast health*. 2015 ;11(1):1.

Data Collection Proforma

Sr. #: _____ Name: _____ Age: _____ Gender: _____

Marital status: _____ Education status: _____

Residence: _____ Contact #: _____ ,

History of smoking: yes/no, family history of any cancer:
 yes/no _____ 1st degree: _____ 2nd degree: _____ 3rd
 degree: _____, Caste: _____, children: _____ Breast fed: yes/no,

Age of menarche: _____, H/O contraceptive use: _____

Consanguineous marriage: yes/no _____

Menopause: yes/no H/O alcohol use: yes/no, H/O smoking:

Chronic liver disease: yes/no

Chronic renal failure: yes/no

Tuberculosis: yes/no

Inflammatory bowel disease: yes/no

Autoimmune disease: yes/no

Previously treated any cancer disease: yes/no

Breast cancer with pregnancy: yes/no

Diagnosis (histopathology) _____,

Histological grade: I _____, II _____, III _____

Receptors: ER _____ PR _____ Her 2 neu _____ others _____

Stage _____ Chemo status _____

Surgery type _____ Radiotherapy _____

Variable	Group A (grisotti flap)		Group B (reverse mirror grisotti flap)	
Flap viability (A-D)	At 48 hours	On 7 th post-op day	At 48 hours	On 7 th post-op day
Cosmetic outcome (visual analogue scale)				
Seroma formation On 7 th post-op day	Yes / No		Yes / No	

Informed Consent Form

COMPARISON OF OUTCOME BETWEEN GRISOTTI FLAP VERSUS REVERSE MIRROR GRISOTTI FLAP FOR CENTRAL QUADRANT BREAST TUMORS.

The doctor has explained me about my disease. The research modalities required for treating my tumour have been thoroughly explained to me. As this research work requires the utilization of either grisotti or reverse mirror grisotti flap technique, therefore I allow the doctor to utilize any of these procedures on me.

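### Flap viability is an ordered A–D grade tested by an order-blind chi-square, and the definition leaves open whether grade B is viable

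*Protocol*

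**What the plan says.** Flap viability is the first outcome named in the protocol's Objectives. Operational Definitions, item 4, defines it as "Absence of necrosis of new areola formed as seen clinically at 48 hours and 7th day postoperatively" and then lists four grades of rising severity. The first three read "A (None): No necrosis", "B (Color Change): Color change suggesting impaired perfusion or ischemic injury" and "C (Partial Thickness): Partial thickness skin flap necrosis resulting in wound breakdown"; grade D is full-thickness necrosis.

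The Data Collection Proforma has one field for this outcome, "Flap viability (A-D"), completed at 48 hours and on day 7. It has no viable yes/no box, whereas seroma is recorded as yes or no.

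The data analysis section treats the grade as categorical: "Qualitative data (tumor size, flap viability and seroma formation) will be expressed as frequencies and percentages". It assigns the test: "Chi square (χ^2) test will be used to compare between groups for qualitative data". It adds that the association between procedure and the clinical outcome variable, which it does not name, will be "assessed by using Odds Ratio (OR) with 95% confidence interval (CI"). It names no ordinal method and no cut-point.

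**The concern.** Two things are fixed badly, and they affect each other.

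**Order.** A Pearson chi-square on four grades gives the same p-value whichever way the columns are arranged. It spends three degrees of freedom looking for any difference, so a consistent move towards milder or worse grades is easier to miss than with a test that uses the order.

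**Grade B.** If the chi-square is meant for a two-way table, or if the odds ratio covers flap viability, the grades must be split. Adjoining lines of the definition support two splits. Because only C and D are described as necrosis, B could be viable. Because only A carries the label of no necrosis, B could be non-viable. The recorded data cannot settle this.

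At stake is the first-named outcome. Its result may depend on a choice that the protocol leaves open and that could be made after the data are seen.

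**Working it through.** **Inputs from the protocol.** 53 patients per arm (Sample Size); significance at p<0.05, taken as two-sided because the sample size uses 1.96; grades A to D (Operational Definitions, item 4). The protocol's own figure reproduces: n = 1.96² × (0.90×0.10 + 0.95×0.05) / 0.10² = 3.8416 × 0.1375 / 0.01 = 52.82, rounded up to 53 per arm, 106 in total. That calculation uses satisfaction rates. No flap-viability rate is given, so every grade distribution below is an assumption.

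**1. Does the placing of grade B matter?** Take illustrative A/B/C/D counts of 43/4/4/2 in group A and 33/14/4/2 in group B.

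- B counted as non-viable: 20/53 (group B) vs 10/53 (group A). Odds ratio = (20×43)/(33×10) = 2.61. SE of the log = √(1/20 + 1/33 + 1/10 + 1/43) = 0.451, so the 95% CI is 1.08 to 6.31. Chi-square = 106 × (20×43 − 33×10)² / (53×53×30×76) = 4.65, p = 0.03.
- B counted as viable: 6/53 vs 6/53. Odds ratio 1.00 (0.30 to 3.33), p = 1.0.
- All four grades: expected counts per arm are 38, 9, 4 and 2, so chi-square = 2×25/38 + 2×25/9 = 6.87 on 3 df, p = 0.08. Mann-Whitney on the same table gives p = 0.06.

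The direction can also reverse. With 40/8/3/2 (group A) vs 46/1/4/2 (group B), the odds ratio is 0.47 with B non-viable and 1.23 with B viable.

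**2. Power for a consistent shift.** A common odds ratio of 3 is applied at every cut: odds of a worse grade in the other arm = odds in the first arm ÷ 3 (better) or × 3 (worse). For example, 70/15/10/5% becomes 87.5/6.9/3.8/1.7%: for grades B–D the odds are 0.30/0.70 = 0.429, and 0.429/3 = 0.143, which is 12.5%. Simulation with 53 per arm, two-sided 5%, uncorrected Pearson chi-square and tie-corrected Mann-Whitney:

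| First arm A/B/C/D | Other arm | Chi-square, 4 grades | Mann-Whitney | 2×2: A vs B–D | 2×2: A/B vs C/D | Splits disagree on p<0.05 |
|---|---|---|---|---|---|---|
| 70/15/10/5% | better | 41% | 61% | 61% | 36% | 35% |
| 80/10/7/3% | better | 26% | 46% | 45% | 24% | 30% |
| 70/15/10/5% | worse | 66% | 82% | 79% | 67% | 24% |
| 80/10/7/3% | worse | 56% | 74% | 74% | 54% | 30% |

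Part of the gap is small-sample conservatism of the chi-square in sparse cells. With permutation p-values for both tests, the two other-arm-better rows become 45% vs 60% and 33% vs 43%.

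**3. No true difference.** With 85/8/5/2% in both arms, the four-grade chi-square rejects in 3.2% of trials; with 92/4/3/1%, in 2.1%. It is conservative, not invalid. The chance that at least one of the two splits gives p<0.05 is about 8% in both cases.

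**4. Where the ordinal test does not win.** If the arms differ only in severity among affected flaps (80/17/2/1% vs 80/4/9/7%), Mann-Whitney has 6% power and the four-grade chi-square about 72%. If they differ only in colour change (80/10/7/3% vs 60/30/7/3%), the figures are 52% and 60%.

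**The case against.** The strongest reply is that the chi-square is a legitimate test for categorical data, so the order point is about efficiency and not error. The preferred test is also not uniformly better, as step 4 shows. An odds ratio of 3 is generous: at 2 (other arm better), power is 19% vs roughly 32% from the first distribution and 13% vs 24% from the second, so sample size becomes the main limit. A 2×2 test of A against B–D does as well as Mann-Whitney in the two other-arm-better scenarios, and the label on grade A gives that split some textual support. The example puts the whole difference in grade B. Disagreement between splits is not an error rate, since they are different endpoints. The odds-ratio sentence does not name flap viability, and a cut-point could be fixed in a SAP.

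Most of this stands as limits on size: the test is valid, the rates are assumed, and the odds-ratio part is conditional. It does not remove the point. The protocol itself fixes the test and carries the two conflicting wordings, so this is more than a detail left to a SAP. The conflict over grade B needs no assumed rate. A split chosen after the data are seen raises the false-positive rate, which is a matter of validity and not only of efficiency.

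**Conclusion.** The concern holds. The only recorded form of flap viability is an ordered grade, the only test assigned to it ignores order when run on the four grades, and the definition supports two incompatible splits.

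Under the assumed rates and a common odds ratio of 3, the four-grade chi-square gives up 16 to 20 percentage points of power against Mann-Whitney (10 to 15 points with permutation p-values, other arm better). The two splits lead to different significance conclusions in 24% to 35% of such trials, and free choice between them takes the nominal 5% false-positive rate to about 8%. The power loss applies to a consistent shift and reverses for the patterns in step 4. How much grade B matters depends on how many B flaps occur, which the protocol does not say. This should be corrected before data are seen; it does not make the planned test invalid.

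**What to change.** - In Operational Definitions, item 4, reconcile the definition with the grade labels. The investigators state before any data are seen which grades count as viable, and that single split is used for every two-way test and odds ratio on flap viability.
- In the data analysis section, name an ordinal comparison of the A–D grade as the main analysis of flap viability: Mann-Whitney with an exact or permutation p-value, or a proportional-odds model. Because the grade is recorded twice, state in advance whether the 48-hour or the day-7 grade is analysed; the investigators choose.
- Report the A–D frequencies by arm beside the ordinal result.

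The cost is two sentences in the analysis section and one line in the definition, with the same data and software. The drawback is that an ordinal result is read as a shift in grade and has little power for a difference confined to severity among affected flaps. Showing the frequencies keeps such a pattern visible.
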